## physIQ Alert System – Ileostomy

Patients:

Any positive symptom (dehydration, infection, or obstruction)
≥1200 ml ostomy output over one day
A high risk alert
A predefined number of standard alerts in a day

Table 4: PhysIQ alerts system for CAPE navigator or monitoring nurse for Ileostomy

For ileostomy the thresholds for the high-risk alerts and the number of standard alerts may be changed from patient to patient based on how each case progresses and the density and frequency of alerts. Determining the optimal thresholds for these two types of alerts will be a key aim of this study. The goal is again maximizing signal while minimizing noise.

If any of these conditions listed in Table 4 are met the monitoring nurse will call the patient and go through a predefined note with the following data elements and questions.

Infection Symptom
 
 
a) Fever
 
b) Dysuria
 
c) Redness at ostomy site
 
d) Drainage or swelling at ostomy site
 
e) Other (Free Text)
 

Obstruction Symptom
 
 
a) Nausea
 
b) Vomiting
 
c) Bloating
 
d) Decreased or no ostomy output
 
e) No gas through ostomy
 

Dehydration Symptom
 
 
a) Lightheadedness
 
b) Dry mouth
 
c) Low or dark urine output
 
d) Dizziness
 
e) Increased ostomy output
 

Symptom Change (Obstruction, Dehydration, Infection) [This can show up if any symptom is picked]
 
 
1. New
 
2. Worsening
 
3. Stable
 
4. Improving
 
5. Resolved
 

Ostomy output
 
 
a) 500-1200cc
 
b) >1200cc
 
c) <500cc
 

Is patient NPO? Yes/No

Is patient on antibiotics? Yes/No

Patient is on stool thickening regimen?
 
 
a) None
 
b) Metamucil powder 1 tsp bid
 
c) Imodium 2mg bid w/ meals (20 mins before meals)
 
d) Imodium 2mg qid w/ meals (20 mins before meals)
 
e) Imodium 4mg qid w/ meals (20 mins before meals)
 
f) Stool thickening managed by clinical team
 

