#### **FOLLOWUP PLAN**

1. Case Communication to Clinical RN
2. Case Communication to Ostomy RN
3. Call Clinical RN
4. Call Ostomy RN
5. Consider Call Clinical RN
6. Evaluate trend of ostomy output
7. Stool thickening initiation Metamucil powder 1 tsp bid
8. Stool thickening escalation Imodium 2mg bid w/ meals (20 mins before meals)
9. Stool thickening escalation Imodium 2mg qid w/ meals (20 mins before meals)
10. Stool thickening escalation Imodium 4mg qid w/ meals (20 mins before meals)
11. Stool thickening escalation management by clinical team
12. IV fluids administration
13. Consider IV fluids administration
14. Consider Lab tests BMP, Mag, Phos
15. Consider Lab test CBC
16. Advance Diet as Tolerated (Clear liquids for 6 hours and then advance as tolerated to low residue diet)
17. Continue NPO status
18. Possible urgent clinic evaluation
- 19. Assess for home visit**

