#### **LOGIC:**

- a) MCI, Afib w/ RVR, Tachycardia, Tachypnea (1, 3, 6)
- b) Other physiologic alert (5)
- c) Ostomy output >1200cc and patient on no stool thickening regimen (1, 5, 7, 13)
- d) Ostomy output >1200cc and patient on metamucil stool thickening regimen (1, 5, 13, 8)
- e) Ostomy output >1200cc and patient on imodium 2mg bid stool thickening regimen (1, 5, 13, 9)
- f) Ostomy output >1200cc and patient on imodium 2mg qid stool thickening regimen (1, 5, 13, 10)
- g) Ostomy output >1200cc and patient on imodium 4mg qid stool thickening regimen (1, 3, 13, 11)
- h) Ostomy output <500cc (1, 3)
- i) Has ANY Obstruction symptom, NEW, or WORSENING Obstructive Symptom, Patient not NPO (1, 3, 14)
- j) Has ANY Obstruction symptom, RESOLVED Obstructive Symptom, Patient not NPO (1)
- k) Has ANY Obstruction symptom, NEW or WORSENING Obstructive Symptoms, Patient NPO (1, 3, 14, 17)
- l) Has ANY Obstruction symptom, STABLE or IMPROVING Obstructive Symptoms, Patient NPO (17)
- m) Has ANY Obstruction symptom, RESOLVED Obstructive Symptoms, Patient NPO and Ostomy output 500-1200 (1, 3, 16)
- n) Has ANY Obstruction symptom, RESOLVED Obstructive Symptoms, Patient NPO and Ostomy output >1200, patient not on stool thickening regimen (1, 3, 16)

- o) Has the following Infectious symptoms (Redness at ostomy site, Drainage or swelling at ostomy site), NEW OR WORSENING Infectious Symptoms, Patient not on antibiotics (2, 4, 15)
- p) Has the following Infectious symptoms (Redness at ostomy site, Drainage or swelling at ostomy site), RESOLVED Infectious Symptoms, Patient not on antibiotics (2)
- q) Has the following Infectious symptoms (Redness at ostomy site, Drainage or swelling at ostomy site), NEW OR WORSENING Infectious Symptoms, Patient on antibiotics (2, 4, 15, 18)
- r) Has the following Infectious symptoms (Redness at ostomy site, Drainage or swelling at ostomy site), RESOLVED Infectious Symptoms, Patient on antibiotics (2)
- s) Has the following Infectious symptoms (Fever, Dysuria or Other), NEW, WORSENING, IMPROVING, OR STABLE Infectious Symptoms, Patient not on antibiotics (1, 3, 15)
- t) Has the following Infectious symptoms (Fever, Dysuria or Other), RESOLVED Infectious Symptoms, Patient not on antibiotics (1)
- u) Has the following Infectious symptoms (Fever, Dysuria or Other), NEW OR WORSENING Infectious Symptoms, Patient on antibiotics (1, 3, 15, 18)

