- v) Has the following Infectious symptoms (Fever, Dysuria or Other), RESOLVED Infectious Symptoms, Patient on antibiotics (1)
- w) Has ANY Dehydration symptom, NEW, or WORSENING Dehydration Symptom, Patient not NPO (1, 3, 12, 14)
- x) Has ANY Dehydration symptom, STABLE OR IMPROVING Dehydration Symptom, Patient not NPO (1, 5, 13)
- y) Has ANY Dehydration symptom, RESOLVED Dehydration Symptom, Patient not NPO (1)

Table 5: CAPE Navigator or monitoring nurse alerts system for clinical team for Ileostomy

Table 5 will be configured into a note template within EPIC that allows for data elements to be captured and have all the logics built in to automatically highlight the recommended options for the monitoring nurse. The EHR smart note will be tested out by the research team to ensure the logic is correct.

If patients have any high risk alerts (MCI, Afib with RVR, Tachycardia, Tachypnea), the monitoring nurse will route a note and call clinical RN and evaluate the trend of ostomy output. All other physiological alerts will result in consideration call to clinical RN.

If patient ostomy output  $>1200\text{cc}$  and patient not on stool thickening regimen yet, the monitoring nurse will send note and call clinical RN, consider IV fluids administration and start stool thickening regimen escalation. Monitoring RNs will call clinical RNs for guidance on IV fluid administration guidance. The stool regimen escalation can occur daily while the output is  $\geq 1200\text{ml}$  in 24 hours. There is no monitoring nurse de-escalation protocol, and this will be performed by the clinical team. If a patient is non-adherent to Metamucil and/or Imodium and output is  $\geq 1200\text{ml}$  in 24 hours, medications will be maintained without escalation and patient will be counseled on the importance of adherence to medications. If the output continues to be greater than  $\geq 1200\text{ml}$  in 24 hours and there are no further options for escalation, the monitoring nurse will call the clinical care team for further guidance.

If ostomy output is  $<500\text{cc}$ , monitoring nurse will route note and call clinical RN. If patient has any new or worsening obstruction symptom but **not NPO** yet, monitoring nurse will route note and call clinical RN, and consider lab tests (BMP, Mag, Phos). If the obstructive symptoms resolve while patient is NPO, home health RNs will route note to clinical RN.

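### Table 5's smart note has no adherence field, so for a non-adherent patient it highlights the Imodium step-up that the narrative bars and never prompts the required counselling

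*Protocol*

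**What the plan says.** All of this is in Protocol section 2.2, in Table 5 and the text around it.

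- **How the note is used.** When an alert condition is met, "the monitoring nurse will call the patient and go through a predefined note with the following data elements and questions". The text after Table 5 says the template will "have all the logics built in to automatically highlight the recommended options for the monitoring nurse".
- **What the note records about stool thickening.** There is one field, "Patient is on stool thickening regimen", with six options: none, Metamucil, three Imodium levels, or managed by the clinical team.
- **What the logic does.** For output above 1200 cc, rows c to g each take one regimen level. Rows d, e and f give items 8, 9 and 10, the successive Imodium steps. Row g, at the top Imodium level, gives item 11, which passes further escalation to the clinical team.
- **What the narrative adds.** Escalation may happen daily while output stays at or above 1200 ml in 24 hours, with one exception. It opens "If a patient is non-adherent to Metamucil and/or Imodium and output is" at or above that level, and its instruction is that "medications will be maintained without escalation and patient will be counseled on the importance of adherence to medications".

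**The concern.** The exception and the table give different instructions for the same patient. The narrative holds the dose and requires counselling. The table moves to the next Imodium level and does not mention counselling. The table is what the nurse will see, because it drives the automatic highlighting.

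Two things are at stake. The first is consistent delivery of the intervention: whether a non-adherent patient is held and counselled or stepped up would depend on the nurse remembering a rule that the note does not show. The second is the study's own product. A finalized EPIC note and finalized nurse alerts to the clinical team are among the listed final specifications, so the mismatch could be carried into them. The note's structured fields also cannot separate high output despite treatment from high output without it, which matters when the escalation rules are reviewed.

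**Working it through.** There is no plan figure to reproduce. The check sets Table 5 beside the narrative rule.

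**Does any part of Table 5 carry adherence?**

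- Data elements: infection, obstruction and dehydration symptoms, symptom change, ostomy output, NPO status, antibiotics, stool thickening regimen, and alerts. That is 9, of which 0 record adherence.
- Logic rows a to y: 25, of which 0 use adherence as a condition.
- Follow-up items: 19, of which 0 are to keep the regimen and counsel.

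**What does the note highlight for a non-adherent patient with output above 1200 cc?** This output level meets both the table's strict threshold and the narrative's inclusive one, so the difference between them does not affect the trace.

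| Prescribed regimen | Row | Items highlighted | Stool-thickening item | Narrative requires |
|---|---|---|---|---|
| Metamucil | d | 1, 5, 13, 8 | Imodium 2 mg bid | hold and counsel |
| Imodium 2 mg bid | e | 1, 5, 13, 9 | Imodium 2 mg qid | hold and counsel |
| Imodium 2 mg qid | f | 1, 5, 13, 10 | Imodium 4 mg qid | hold and counsel |
| Imodium 4 mg qid | g | 1, 3, 13, 11 | clinical team manages | hold and counsel |

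**Result.** The barred step is highlighted in 3 of 3 cases in rows d to f. The required counselling is prompted in 0 of 4 cases in rows d to g. Row g does not highlight a higher dose, so it lacks only the counselling prompt.

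**Would the planned testing find this?** The research team will test the note to confirm that its logic is correct. A build that follows Table 5 exactly would pass a test against Table 5, because the adherence rule is not in the table. It would be found only if the test also covered the narrative.

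**The case against.** The strongest reply is that the table gives the general ladder and the narrative gives the exception, so nothing is reversed. The narrative adds other rules that the table lacks, such as leaving de-escalation to the clinical team. The highlights are not exhaustive either: item 19, the home-visit assessment, appears in no row. They are recommendations, and the nurse is speaking with the patient and can leave items 8 to 10 unchosen. Rows d to f keep item 1, so the clinical RN is informed, and item 5, which has the nurse consider a call. The note is provisional, and finalizing it is part of the study's purpose. Adherence is not invisible to the study as a whole: medications and nursing notes are accessible under the consent terms, and the provider endpoint interview asks about taking medications as prescribed.

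Most of this stands, and it is why the consequence is modest. It does not remove the mismatch. An exception that changes the output of three rows needs a field that can trigger it, and the note has none.

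Two stronger readings are tempting, but the documents do not support them.

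- **A patient not taking the drug is entered as on no regimen.** A reader might infer that row c then fires and highlights item 7, "Stool thickening initiation Metamucil powder 1 tsp bid". The narrative for row c speaks of a patient not yet on a regimen, meaning one not started. The non-adherence rule speaks of medications being maintained, so that patient still counts as on a regimen. Both point to the prescribed regimen, and row c is not part of this point.
- **The patient is exposed to a higher dose.** The ladder runs 2 × 2 = 4, 2 × 4 = 8 and 4 × 4 = 16 mg of Imodium per day, so a reader might infer increases of 4, 4 and 8 mg per day in rows d, e and f. These are gaps between prescribed levels on an advisory list. They are not doses taken by a patient who is, by definition, not taking the regimen as instructed.

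**Conclusion.** The point holds for Table 5 and its narrative. Built as written, the smart note recommends the next Imodium step in each of the three rows where the narrative forbids escalation for a non-adherent patient, and it prompts counselling in none of rows d to g. The consequence is modest: the highlight can be overridden and the case is still communicated to the clinical RN. It is nevertheless worth correcting before the note is finalized, because the change is small.

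The conclusion rests on reading the regimen field as the prescribed regimen, which the narrative wording favours but the field itself does not state. The documents give no non-adherence rate, so nothing is claimed about how many of the 10 patients would be affected, and no endpoint or sample-size figure is touched. The process map in Figure 2 is not available in the text reviewed, so the conclusion does not extend to whether that map has an adherence branch.

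**What to change.** 1. State that the regimen field means the prescribed regimen.
2. Add one yes/no field on whether the patient is taking the current regimen as instructed.
3. Add one follow-up item: maintain the regimen and counsel on adherence.
4. In rows d, e and f, highlight items 8, 9 and 10 only if the answer is yes. If it is no, highlight the new item instead. Keep items 1, 5 and 13 in either case.
5. In row g, keep items 1, 3, 13 and 11, and add the new item if the answer is no.
6. Leave row c unchanged.

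Communication with the clinical RN, consideration of IV fluids and handover to the clinical team are then never suppressed. The logic test should include a non-adherent case for each of rows d to g. The build cost is one definition, one field, one item and conditions in four rows. The running cost is one extra question per call.

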# RESEARCH PLAN

## 1.1 Summary

We propose to test our central hypothesis that readmission and post-discharge utilization in high risk medical and surgical patients can be reduced by using a vendor platform (PinpointIQ from the company physIQ) that involves wearable sensors (Vital Patch) that collect real-time, continuous ambulatory vital signs, a mobile device that collects patient reported outcomes and machine learning algorithms in the cloud that identify patients at risk of physiologic perturbation. Data from this vendor platform will be tied to operational workflows at NorthShore that involve a monitoring nurse who then conveys information to the clinical team as necessary in a cascading alert system.

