Postoperative ileostomy patients are frequently readmitted because of physiologic perturbation and has readmission rates between 15-30% at NorthShore. Ileostomy patients are readmitted because of dehydration. There has been early work establishing the predictive potential of multivariate physiological telemetry (pinpointIQ) from a wearable sensor providing accurate early detection of impending rehospitalization for postoperative ileostomy with a predictive accuracy comparable to implanted devices. This population may benefit from remote continuous monitoring of vital signs tied to a cascading alert system to identify patients at risk of impending decompensation. There is limited literature looking at how continuous monitoring, ambulatory wearable devices can improve outcomes in high risk patients.

We propose conducting a mixed-methods study that will use a wearable device to collect ambulatory physiological data analyzed by a machine-learning algorithm to identify readmission risk. The alerts will be tied to a cascading escalation pathway that involves monitoring nurse, mid-level providers, specialists, and surgeons. We describe the quantitative and qualitative aspects of the study in detail below.

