# QUANTITATIVE

## 2.1 Quantitative Research Aims – Ileostomy Cohort

Aim 1: Determine if wearable technology deployed for 30 days in a high-risk patient population can augment 30-day readmission risk prediction and improve care processes via an escalating feedback protocol.

Aim 2: Understand and finalize thresholds and criteria for alert system at the levels of Vital Patch, physIQ's pinpointIQ, monitoring RNs for ileostomy patients

Aim 3: Finalize process maps and workflows for nurse navigators and clinical care teams that optimize identifying high risk patients while minimizing provider burden

Aim 4: Calculate the return on investment of the remote monitoring solution

Aim 5: Perform a deep analysis of the full process to understand effectiveness, feasibility, efficiency and bottlenecks

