## 2.2 Experimental Plan and Methods

The goal of the study is to reduce readmission rates for high risk medical and surgical patients. The goal of the study is to understand how physIQ's platform Pinpoint IQ with a cascading set of alerts including the wearable device alerts, patient reported metrics, CAPE navigator or monitoring nurse alerts can be developed and improved upon to reduce the incidence of 30 day readmission. We will be enrolling 10 colorectal (post ileostomy formation) patients who will be using a standardized set of cascading alerts that have been fine tuned with the goal of reducing decompensation and 30-day readmissions.

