Figure 2: Process map for Ileostomy Patients

If care is escalated to the clinical care team which includes ostomy RNs, clinical RNs, and Physicians, the care team will pursue various interventions including counseling, altering medication therapy such as antibiotic therapy, procedures such as debridement or drainage, urgent visits to the colorectal surgery clinic ideally within 72 hours, and if no other available options readmission. These workflows will be left

to the discretion of the clinical care team given the nuance in taking care of these high-risk patients and the existing relationship and prior history with these providers. There are some standardized workflows that will be followed by the care team that are of note. Infusions of IV fluids will occur if the patient has  $\geq 1200$  ml of ileostomy output and dehydration symptoms. If these symptoms are identified, the goal will be to have monitoring nurse perform infusion at the patient's home. Also, all messaging from the monitoring nurses will be forwarded to the colorectal/ileostomy pool per protocol and logic in Table 5 to create the most rapid response back to the patient if required.

The final specs of the study will include:

1. Optimal inclusion/exclusion criteria.
2. Specific thresholds for high risk alerts for each use case
3. Specific thresholds for standard alerts (likely use physIQ standard thresholds)
4. Finalized physIQ alerts to CAPE navigators and monitoring nurse
5. Finalized CAPE navigator and monitoring nurse alerts to clinical care team
6. Finalized EPIC note
7. Finalized process maps
8. Finalized workflows by clinical care team
9. Discussion with physIQ to optimize the pinpointIQ portal to best support the CAPE navigators and monitoring nurse

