The recruitment goals for this study is 10 ileostomy patients each for 30d of monitoring to evaluate if the remote monitoring technology from physIQ and cascading alert system and process can reduce 30-day readmissions. We will also perform economic calculations to determine if there is return on investment for this workflow tied to remote monitoring. Finally, we would like to do an in-depth analysis of the process to understand effectiveness, feasibility, efficiency, and bottlenecks. Some of the questions we would like to understand include: 1) What component of the cascading alert system provides the highest effectiveness of identifying patients at risk? 2) Can we reduce the number of monitored days and still effectively reduce 30 days of readmission? 3) Are there specific subgroups of patients who may benefit from the remote monitoring solution, or alternatively, are there subgroups who do not benefit from the remote monitoring solution? 4) Can we take our process maps and perform process simulation with data from the study and process mining to optimize our process and identify chokepoints with our current flow.

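### Ten monitored patients with no comparator described are recruited to evaluate a reduction in 30-day readmissions, which this design is very unlikely to show and could not attribute to monitoring

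*Protocol*

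**What the plan says.** The recruitment paragraph that closes Protocol Section 2.2 sets a goal of 10 ileostomy patients, each monitored for 30 days, "to evaluate if the remote monitoring technology from physIQ and cascading alert system and process can reduce 30-day readmissions". Among the questions it then lists are "Can we reduce the number of monitored days and still effectively reduce 30 days of readmission" and "Are there specific subgroups of patients who may benefit from the remote monitoring solution". The same paragraph announces a return-on-investment calculation and an analysis that covers effectiveness.

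Section 1.1 states the purpose in similar terms: "We propose to test our central hypothesis that readmission and post-discharge utilization in high risk medical and surgical patients can be reduced". The opening of Section 2.2 is mixed. One sentence reads "The goal of the study is to reduce readmission rates for high risk medical and surgical patients", and the next describes the goal as learning how the platform and its cascade of alerts can be developed and made better.

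The rest of the protocol describes development work. None of the five aims in Section 2.1 lists a reduction in readmissions. Aim 1 concerns risk prediction and care processes, Aim 2 is to "Understand and finalize thresholds and criteria for alert system", and Aim 3 concerns process maps and workflows. Aim 4 is return on investment. Aim 5 is a process analysis that names effectiveness. The outputs listed late in Section 2.2 include "Finalized workflows by clinical care team". Section 3.2 speaks of hypotheses for further study and of contributions to a proposal for a follow-up randomized trial.

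The only readmission rate is in Section 1.2, where this population "has readmission rates between 15-30% at NorthShore". That sentence gives no time window, and the rate is not named as a reference for any comparison.

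**The concern.** The recruitment sentence ties an efficacy question to these 10 patients. Every enrolled patient is monitored, and no control group, randomization or historical comparator is described. The intervention is also not held fixed: Section 2.2 (physIQ Alert System – Ileostomy) allows alert thresholds to change from one patient to the next. That suits development, but not the estimation of an effect.

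Read as worded, the protocol would let a low readmission count be reported as evidence that monitoring reduces readmission, although low counts are fairly common with no effect. The subgroup and shorter-monitoring questions carry the same risk. In a single monitored cohort, a subgroup with few readmissions may simply be at low risk, which is not the same as benefiting. Asking whether fewer monitored days still reduce readmission presupposes that a reduction has been shown.

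**Working it through.** The protocol gives no calculation behind the figure of 10, so there is none to reproduce. The check is what 10 patients can show.

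**Inputs from the protocol.** n = 10 (Section 2.2); background rate 15% to 30% (Section 1.2).

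**Assumptions, not in the protocol.** The 15-30% is a 30-day rate and applies to patients who meet Section 4.2.1 (discharged with home health services, not to a subacute facility). Tests are exact binomial; a one-sided 5% level and a two-sided 95% interval are both shown. The illustrative effect is a halving of the rate.

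**Expected count with no effect.** n × p = 10 × 0.15 = 1.5, and 10 × 0.30 = 3.0.

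**Low counts with no effect.** P(0) = (1 − p)^10 and P(1) = 10 p (1 − p)^9.

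| True rate | P(0 of 10) | P(0 or 1 of 10) |
|---|---|---|
| 15% | 0.197 | 0.544 |
| 20% | 0.107 | 0.376 |
| 25% | 0.056 | 0.244 |
| 30% | 0.028 | 0.149 |

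For example, at 15%: 0.85^10 + 10 × 0.15 × 0.85^9 = 0.197 + 0.347 = 0.544.

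**Exact two-sided 95% intervals (Clopper-Pearson).** For 0/10 the upper limit is 1 − 0.025^(1/10) = 0.308, so the interval is 0 to 30.8%. For 1/10 it is 0.3% to 44.5%. Neither excludes any rate between 15% and 30%.

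**One-sided 5% level.** The smallest fixed rate that 0/10 rejects is 1 − 0.05^(1/10) = 0.259. So 0/10 is nominally significant against 30% (p = 0.028) but not against 25% (0.056), 20% (0.107) or 15% (0.197). For 1/10 the one-sided upper limit is 39.4%, so it rejects nothing in the range.

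**Chance of that one favourable result.** If monitoring halved 30% to 15%, P(0/10) = 0.85^10 = 0.197. For 0/10 to occur with probability 80%, the true rate would have to be at most 1 − 0.80^(1/10) = 0.022, which is 1 − 0.0221/0.30 = 93% below 30%.

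**For scale only.** With 80% power and a one-sided 5% level (both assumed), an exact single-arm test of a halving against a fixed rate needs about 49 patients for 30% to 15% (9 or fewer readmissions: probability 0.048 at 30%, 0.809 at 15%). It needs about 118 for 15% to 7.5% (11 or fewer: 0.049 at 15%, 0.825 at 7.5%). Such a test would still have no concurrent control.

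**The case against.** The strongest reply is that this is a development study. The sentence after the one quoted from the opening of Section 2.2 already gives a development goal. The aims, the listed outputs and the mention of a randomized trial proposal point the same way. The subgroup and shorter-monitoring questions are offered as matters of interest within a process analysis, with no test or success criterion attached. The statistical analysis plan is not at hand and could name a historical reference.

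Much of this stands. Section 2.2 should be read as mixed, not as an efficacy goal throughout, and 10 patients are not too few for development. The reference to medical and surgical patients in Section 1.1 and at the start of Section 2.2 is wider than this cohort and allows a programme-level reading. The recruitment sentence allows no such reading, because it gives the purpose of these 10 patients. A historical reference named elsewhere would supply neither a concurrent control nor adequate power.

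A reader might infer that no analysis of 10 patients could ever point to a reduction. The figures do not support that: 0/10 against a fixed rate above 25.9% would do so nominally, one-sided. A reader might also infer that the sample size is itself an error, or that the reduction question can simply be passed to a planned randomized trial. The protocol supports neither. The development aims do not need more patients, and Section 3.2 foresees only contributions to a trial proposal.

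**Conclusion.** The point holds as a mismatch between the stated purpose and the design. With 10 monitored patients and no comparator described, the study is very unlikely to show a reduction in 30-day readmissions, and it could not attribute one to monitoring. The single nominally favourable outcome, 0/10 against a fixed rate above 25.9%, has a 19.7% chance even if 30% is halved. On a two-sided 95% interval, no result excludes a rate in the 15-30% range from above. One readmission or none is unremarkable with no effect.

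These figures depend on reading the background range as a 30-day rate for the eligible patients, on the assumed test levels, and on the halving as an illustration. The absence of a comparator matters whatever the rate. The return-on-investment and effectiveness analyses (Aims 4 and 5) lean on the same unshown effect.

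**What to change.** 1. In the recruitment paragraph of Section 2.2, state that the 10 patients are recruited to assess feasibility and to refine alert thresholds, workflows and process maps. State that the number readmitted within 30 days will be reported descriptively with its exact 95% confidence interval.
2. Add there that no conclusion of reduced readmission, subgroup benefit or adequacy of shorter monitoring will be drawn from these patients. Mark these questions, and the return-on-investment and effectiveness analyses (Aims 4 and 5), as exploratory. Say that the results may inform the proposal for a follow-up randomized trial.
3. In Section 1.1, label the reduction hypothesis as the programme's hypothesis, not tested in this study. At the start of Section 2.2, keep the development sentence and bring the goal sentence before it into line.

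The cost is protocol wording only: no extra patients, visits or data, and the sample size stays at 10. The downside is a weaker headline claim.
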